2.4.1 Longitudinal Survey Study

The digital participation survey (Proxy or Self/supported completion as appropriate) will be administered to a convenience sample of 400 people with intellectual disabilities at two time points eight months apart (+/-1 month). This sample size will enable digital health participation for people with intellectual disabilities to be adequately understood across the breadth and heterogeneity inherent in this population. It will also enable a sufficiently powered analysis to identify moderate effect sizes in relation to predictors of digital health participation.

Survey sampling & recruitment

Adults with a diagnosis of intellectual disabilities and the family and paid carers (as proxy participants for people with higher support needs) are the target population. Taking a whole population approach, and to increase geographical diversity, a self-selecting sample of 400 adults with intellectual disabilities will be recruited equally from the four study sites.

Recruitment will be facilitated by partner organisations with established groups of people with intellectual disabilities and links with additional community groups and agencies which contain under-represented groups of people with intellectual disabilities. Birmingham Community Healthcare NHS Foundation Trust will also act as a recruitment centre. Our overall planned accrual rate is 50-60 participants per month across the four study sites (12-15 per site) over seven months to reach our aim of a final sample size of 400 (Note we expect some of the 60 participants from WP1 to participate in WP2 and WP3).

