Descriptive analysis of levels and frequency of digital health participation. A cross-lagged path analysis (CLPM) will investigate changes over time and identify causal relationships between aspects of digital health participation and physical and mental wellbeing, while controlling for demographic and background characteristics (Kenny & Harackiewicz, 1979). By fitting the model with causal crossed lagged pathways in both directions, we can address whether aspects of digital health participation causally precedes physical and mental wellbeing or vice versa in individuals with intellectual disabilities. Sample sizes $N=100 - 400$ are sufficient for structural equation modelling; more specifically, $N=150$ for models including seven or fewer variables with modest communalities (below 0.5) and zero under identified constructs (Hair *et al.*, 2014). We will fit models with and without cross lagged effects and use likelihood ratio tests (specifically, AIC and BIC criterion) to compare these nested models to determine which better fits the data (Kenny & Harackiewicz, 1979). If data is found to be missing at random (MAR), CLPM analyses will default to using full-information maximum likelihood. All models will be reported with robust standard errors and model fit will be evaluated using the comparative fit index (CFI >0.9), Tucker-Lewis Index (TLI >0.9), standard root mean squared residual (SRMR <0.08) and root mean square error of approximation (RMSEA <0.08), (see Wang & Wang, 2012; Hu & Bentler, 1999; Schreiber *et al.*, 2006).

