2.4.2 Comparative study of Digital Health Inequality

A cross sectional comparative study will contrast digital health participation of people with intellectual disabilities to a reference group people without disabilities.

Comparator

A reference group of 200 participants without disabilities will be recruited across the study sites via local advertisement and social media. This referent group will concurrently complete the same Digital Health Participation survey online via Qualtrics. A referent sample of 200 will allow detection of a group difference, $d=0.2812$ (small-medium effect) at 90% power, 2:1 group ratio, and $\alpha=0.05$. Sample size calculations were conducted using G*Power 3.1.9.7. Our overall planned accrual rate for the referent group is 25-30 participants per month across the four study sites (6-8 per site) over seven months to reach our aim of a final sample size of 200.

Primary outcome

Digital health participation levels as developed from the work in WP1 will be used as the primary outcome measure.

Secondary outcome

Level of mental and physical wellbeing will be measured using the EQ5 (Herdman *et al.* 2011).

Comparative study statistical analysis

Descriptive analysis of levels and frequency of digital health participation of the groups (N=600). Between group comparison using general linear model (GLM) of digital health participation of people with intellectual disabilities.

The study will use propensity score weighting (inverse probability weights) to reduce the bias due to confounding variables and ensure sufficient balance across groups. The propensity scores will be generated on the basis of the following variables: geographic region, sex, age band, ethnicity, and deprivation index. In the event that models including the probability weights do not converge, we will explore other approaches to resolve (i.e. direct adjustment as the number of covariates is relatively small).

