2.7 Study Setting and Context

Participants recruited into the WPs will live in a variety of support settings including their own homes, family homes, supported living accommodation, group homes and other congregate settings.

Study site partners for the project (and associated Universities) are:

- Dudley Voices for Choice & The West Midlands Self Advocacy Network, West-Midlands England (LJMU)
- Advocating Together, East-Central Scotland (DU)
- East Kent Mencap, South-East England (UoK)
- People First, North-West England (MMU)

- Birmingham Community Health Care NHS Foundation Trust (BCHCFT) (LJMU)

These partner organisations employ and facilitate self-advocacy in people with intellectual disabilities and will serve as links and contacts with these settings for recruitment and will negotiate and ensure cooperation by supporting organisations for each participant.

3. Participant Selection & Recruitment

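### The 90% power for the group comparison assumes 600 independent responses, although the intellectual-disability group is recruited through organisations and shared settings; no clustering allowance is made and no cluster code is listed

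*Protocol*

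**What the plan says.** The comparative study (section 2.4.2) states that "A referent sample of 200 will allow detection of a group difference" of d=0.2812 "at 90% power, 2:1 group ratio, and $\alpha=0.05". It adds that "Sample size calculations were conducted using G*Power 3.1.9.7". No design effect, ICC or cluster size is mentioned there or elsewhere.

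The intellectual-disability group is "a convenience sample of 400 people with intellectual disabilities at two time points eight months apart" (section 2.4.1), split equally over four sites. On the route in, the same section says: "Recruitment will be facilitated by partner organisations with established groups of people with intellectual disabilities". Linked community groups and agencies are also used. Section 2.7 lists where participants live: their own and family homes, but also "supported living accommodation, group homes and other congregate settings". Paid and family carers may complete the survey as proxies. The carer criterion in section 3.2.1 sets no limit of one person per carer.

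On analysis, the cross-lagged section says "All models will be reported with robust standard errors", and section 2.3.5 says the same of the factor models. Neither names a cluster unit. The general linear model in section 2.4.2 is to report 95% confidence intervals, with no variance estimator stated. The survey content listed in section 2.4.1 includes postcode and level of support need, but no code for home, service or proxy carer. Section 2.4.2 closes by deferring detail to a later statistical analysis plan.

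**The concern.** The planned measure covers access to technology, its use, and support for digital participation (section 2.3.4). People in one home or service plausibly share devices, connection, staff and house rules, and a carer who answers for two people brings the same judgement to both. Responses from such people carry less information than the same number of unrelated responses.

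Two things are at stake. The first is the stated power, which is the only numerical power figure for the survey work. The second is the width of the intervals, both for the gap between groups and for the cross-lagged paths that the protocol intends to read causally. The longitudinal study is the more exposed in principle, because it has no unclustered reference group to dilute the effect. The analysis can be set later, but it needs a variable to cluster on, and that has to be collected with the survey.

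**Working it through.** **Inputs from the protocol.** 400 and 200 participants; d=0.2812 (SD taken as 1); 90% power; alpha 0.05 (section 2.4.2). Sidedness is not stated.

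**1. Reproducing the stated figure.** For independent responses the variance of the difference is 1/200 + 1/400 = 0.0075, so the standard error is 0.0866 and the noncentrality is 0.2812/0.0866 = 3.247. The noncentral t distribution with 598 degrees of freedom, two-sided, gives power 0.9000 and a detectable d at 90% power of 0.2812. The one-sided version gives 0.945 and does not match. The stated figure is therefore the two-sided test on 600 independent responses.

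**2. Clustering in the intellectual-disability group only.** The reference group is recruited by advertisement and social media, so it is left unclustered. With m people per cluster, DEFF = 1 + (m−1)·ICC and the variance is 1/200 + DEFF/400. If only a share s is clustered, the average design effect is 1 + s(m−1)·ICC. The values of m, ICC and s are **assumptions**.

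| m | ICC | share clustered | DEFF | SE | power at d=0.2812 | detectable d at 90% |
|---|---|---|---|---|---|---|
| – | 0 | – | 1.00 | 0.0866 | 90% | 0.281 |
| 3 | 0.05 | all | 1.10 | 0.0880 | 89% | 0.286 |
| 5 | 0.10 | all | 1.40 | 0.0922 | 86% | 0.299 |
| 5 | 0.10 | half | 1.20 | 0.0894 | 88% | 0.290 |
| 10 | 0.10 | all | 1.90 | 0.0987 | 81% | 0.321 |
| 10 | 0.10 | half | 1.45 | 0.0929 | 86% | 0.301 |

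**3. Intervals for the group gap, if clustering were ignored.** The reported standard error would be too small by sqrt(variance/0.0075). With all 400 clustered this is 1.02 (m=3, ICC 0.05), 1.06 (m=5, ICC 0.10) and 1.14 (m=10, ICC 0.10). A nominal 95% interval then covers about 94.6%, 93.4% and 91.4%.

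**4. Cross-lagged paths.** For a path from predictor to outcome, the design effect is about 1 + (m−1)·ICC(predictor)·ICC(outcome), and the true error rate of a nominal 5% test is 2(1 − Φ(1.96/√DEFF)). With outcome ICC 0.10 and all participants clustered:

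| predictor ICC | m=5: DEFF, error rate | m=10: DEFF, error rate |
|---|---|---|
| 0.10 | 1.04, 5.5% | 1.09, 6.0% |
| 0.30 | 1.12, 6.4% | 1.27, 8.2% |
| 1 (constant within a setting) | 1.40, 9.8% | 1.90, 15.5% |

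The cross-lagged predictors are individual participation and wellbeing scores, so the first two rows apply to them. The last row applies only to something identical for everyone in a setting.

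**The case against.** The strongest reply is that the protocol never says its standard errors assume independence. It promises robust standard errors for the factor and cross-lagged models, leaves the variance estimator for the general linear model open and defers detail to a later plan, where a cluster unit could still be named. That stands. A reader might infer that the reported intervals will be too narrow; the document supports this only if clustering is not dealt with. The power figure is different, because it is already fixed in the protocol.

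A reader might also infer that nothing could be repaired later. That goes too far. Postcode is collected, partner organisations hold sampling frames (section 3.3.2), and proxy carers give their own consent (section 3.4). These are partial substitutes. Postcode does not identify a service or a shared carer, and linking recruitment and consent records to survey responses afterwards is more work and less sure than a code in the survey.

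Three further points are fair. Recruitment is by individual expression of interest rather than by enrolling whole homes, and the residential list in section 2.7 starts with people's own and family homes, so the clustered share may be well below all 400. One carer answering for several people is left open, not planned. And an error rate of 10% to 16% for the cross-lagged paths is tempting to quote but needs a predictor that is constant within a setting, which individual scores are not.

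**Conclusion.** The concern holds in a limited form. The 90% power is correct only for 600 independent responses, and the protocol's own recruitment route makes independence doubtful in the group of 400. Under the assumptions shown, the loss runs from about 1 point (89%) to about 9 points (81%). It is 2 to 4 points in the two ICC 0.10 cases if half the group is clustered. The detectable difference rises from 0.281 to at most 0.321. If clustering is ignored, cross-lagged tests between individual scores would run at about 5.5% to 8.2% instead of 5%.

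These sizes rest on assumed ICC, cluster size and clustered share, none of which the protocol gives. They do not undermine the study. The point merits action because the stated power needs a qualification and because a usable cluster code is cheap to collect with the survey and awkward to rebuild afterwards.

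**What to change.** - Add two anonymous fields to the background items in section 2.4.1: one code for the home or service, and one for the proxy carer where there is one.
- Use that level as the cluster unit for the robust standard errors already planned in the factor and cross-lagged models, and for the general linear model. The four sites are too few to serve as clusters for this purpose.
- In section 2.4.2, state that the 90% power applies to independent responses, and give the range above with its assumed ICC, cluster size and clustered share.

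The cost is two short survey fields and a software option. The downside is slightly wider intervals and a less favourable stated power.

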Partner organisations will ensure adequate oversampling to offset participant drop out. The organisations will also support sample replenishment in the case of non-completion of the survey at time 1. Levels of dropout in longitudinal studies with individuals with intellectual disabilities is approximated at 13% (McCarron *et al.*, 2020); however, we will conservatively allow for up to 15% via oversampling (McCarron *et al.*, 2020). To ensure inclusion of under-represented groups (e.g. people with intellectual disabilities from: ethnic minority/global majority groups, with autism, who are older, and who have underlying physical health problems) and groups more at risk of digital exclusion (older; unemployed; living in group settings supported by paid staff; people with greater support needs (via carers) (Anrijs *et al.*, 2022), sample characteristics will be reviewed after 25% of initial survey data collection has been achieved. If insufficient at initial recruitment, a purposive/targeted sampling strategy, facilitated by partner organisations, will be implemented to ensure adequacy of representation. This review process will be repeated once 75% of initial survey data collection is complete.

Longitudinal survey data collection

Prior to data collection, participants and their carers will be invited to attend online training workshops provided within the project to support the survey data collection (Work package 2). Training will be provided by the CI and site/regional PIs alongside the RAs and the CRs with intellectual disabilities.

Participants will choose their preferred modality for survey completion (Paper-based, online completion (housed on Qualtrics), telephone completion, face-to-face completion as an interview with the geographically closest researcher or a known carer). Where appropriate, the survey will be administered by RAs and CR at each study site. Self and carer supported completion will also be offered for data collection. Survey methods are viable for use with people with intellectual disabilities and have been used successfully by applicants previously and in recent large-scale studies (e.g. Caton *et al.*, 2022). Guidance on completion will be

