Financed Project Resources: iPads (& Sim cards), Laptops, ARCGIS, Qualtrics licence. Participant remuneration for time, payment for RAs, third sector partner organisations & co-researcher(s) with intellectual disabilities. PPIE Payment for steering committee members. Translation costs.	WP2. Longitudinal Digital Health Participation Survey. Collation of measures of background, social determinants of health & wellbeing alongside bespoke digital participation survey. Participants across four sites with intellectual disabilities (N=400) complete survey twice (8 month follow up). Workshop to provide survey completion training. Carers, RAs & CR to support survey completion. Quantitative analysis (Cross-lagged PA, CFA).	Analysis of psychometric properties of Digital Health Participation Survey. People with intellectual disabilities to complete survey to provide digital health participation information at two time points. Longitudinal modelling of causal factors influencing digital health participation & wellbeing of people with intellectual disabilities. Development of sampling frame from survey cohort and recruitment of sample of participants with intellectual disabilities for WP3.	Enhanced understanding of how background characteristics, social determinant of health, digital participation & health literacy interact to influence wellbeing amongst people with intellectual disabilities.	Illumination of digital health participation needs of the participants
Supervision & Training: Regarding data collection processes & methods provided to RAs and Co-researcher(s). Training, guidance & ongoing support in survey completion & use of ArcGIS storysharing software. Qualitative analysis training for RAs from PI.	WP2. Comparative survey study. Recruitment of matched referent group of people without intellectual disabilities. Completion of Digital Health Participation Survey by referent group. Comparative analysis to identify inequalities in digital health participation (GLM).	Identification of levels of inequality in digital health participation.	Enhanced understanding of levels of digital & health inequality for people with intellectual disabilities and the factors specific to people with intellectual disabilities which perpetuate & alleviate inequalities and exclusion.	

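### The WP2 longitudinal target of 400 is used for recruitment, for the final sample and for completion of both surveys, which the stated accrual and 15% dropout allowance cannot all satisfy

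*Protocol*

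**What the plan says.** Section 2.4.1 of the protocol gives the number 400 three roles.

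- **Number surveyed at each wave:** the survey is "administered to a convenience sample of 400 people with intellectual disabilities at two time points eight months apart". Appendix 1 repeats this in the WP2 row: "Participants across four sites with intellectual disabilities (N=400) complete survey twice (8 month follow up".
- **Number recruited:** "a self-selecting sample of 400 adults with intellectual disabilities will be recruited equally from the four study sites".
- **Final number:** accrual runs "over seven months to reach our aim of a final sample size of 400".

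The recruitment plan is "Our overall planned accrual rate is 50-60 participants per month across the four study sites (12-15 per site) over seven months".

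On attrition, the same section says "Levels of dropout in longitudinal studies with individuals with intellectual disabilities is approximated at 13" per cent, and then "we will conservatively allow for up to 15% via oversampling". Partner organisations are to replace people who do not complete the survey at time 1. No replacement is described for people lost between the two surveys. No oversampled recruitment figure is given anywhere.

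**The concern.** A sample cannot be 400 at recruitment and 400 at the end if up to 15% may be lost in between. Oversampling would resolve this only if more than 400 people were enrolled, and the accrual plan leaves little room for that. A reader cannot tell whether 400 is the time-1 or the time-2 number.

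Two things depend on the answer. Sites recruit to the monthly rates, and a shortfall against the promised oversampling cannot be repaired once time-1 recruitment closes. The statement in section 2.4.1 that the sample gives enough power for moderate effects of predictors also rests on 400, while the cross-lagged analysis draws its longitudinal information mainly from people with both surveys.

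**Working it through.** **Inputs, all from protocol section 2.4.1:** 50 to 60 participants per month; seven months; target 400; dropout 13% expected and 15% allowed. Appendix 1 supplies the statement that 400 complete the survey twice.

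**Step 1. Can the accrual plan produce 400 at time 1?** Total = rate × 7.
- 50 × 7 = 350 and 60 × 7 = 420.
- The rate needed for 400 is 400/7 = 57.1 per month, which lies inside 50 to 60.

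Read as a time-1 number, 400 is consistent with the plan.

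**Step 2. What does 400 at time 2 require?** Time-1 number = 400/(1 − dropout).

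| Dropout | 400/(1 − d) | More lenient 400 × (1 + d) |
|---|---|---|
| 15% | 470.6, so 471 | 460 |
| 13% | 459.8, so 460 | 452 |

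The accrual maximum of 420 is below all four figures. It is 471 − 420 = 51 short of the first. It would absorb a loss of (420 − 400)/420 = 4.8%, not 15%.

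**Step 3. What accrual would deliver 471?** 471/7 = 67.3 per month over seven months. At the stated rates it would take 471/60 = 7.9 to 471/50 = 9.4 months.

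**Step 4. How many would complete both surveys?** Completers = enrolled × (1 − dropout).

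| Enrolled | At 15% loss | At 13% loss |
|---|---|---|
| 350 | 297.5, about 298 | 304.5 |
| 400 | 340 | 348 |
| 420 | 357 | 365.4 |

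**Step 5. What does this cost in precision?** For an estimate based on two-wave completers alone, the standard error scales with 1/√n. Going from 400 to 340 widens it by √(400/340) = 1.085, or about 8%. Going to 298 widens it by √(400/298) = 1.159, or about 16%.

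**Step 6. Is the comparative power statement in section 2.4.2 affected?** With 400 against 200, d = 0.2812 and two-sided alpha 0.05 (sidedness is not stated and is assumed here), the exact non-central t calculation gives 90.0%. This reproduces the stated 90%. The comparison is cross-sectional with N = 600, so loss at time 2 does not enter it.

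**The case against.** The strongest defence is that 400 simply means time 1. The accrual range then brackets the target, and the model still works with fewer completers: section 2.4.1 cites 100 to 400 as sufficient for structural equation modelling, and 150 for models of seven or fewer variables with modest communalities. Full-information maximum likelihood is planned if data are missing at random, so people with only a time-1 survey would still contribute. This stands, and it limits the consequence. It does not remove the inconsistency, because the final sample size wording and Appendix 1 would still be wrong and the oversampling sentence would have no number behind it.

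A second defence is that extra people may come from elsewhere. Section 2.4.1 expects some of the 60 WP1 participants to join WP2, but does not say that they come on top of the stated accrual, which is described as the overall rate. Even if they did, 471 would need accrual at its maximum every month and at least 51 of the 60. Replenishment does not help, since it is limited to non-completion at time 1. A longer recruitment period might fit within the 19 months given to WP2, but the protocol does not plan one.

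A reader might infer more than the documents support.

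- *That the referent recruitment fails in the same way.* The plan of "25-30 participants per month across the four study sites (6-8 per site) over seven months" gives 25 × 7 = 175 to 30 × 7 = 210, which contains the target of 200. That group is surveyed once, so it has no follow-up loss.
- *That the lower half of the accrual range is itself an error because it gives fewer than 400.* A planning range that brackets its target is consistent with it.
- *That the comparative power is overstated.* It reproduces at the planned 400 and 200. Lower power at lower accrual describes under-recruitment, not a mistake in the plan.

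**Conclusion.** The point holds for the longitudinal survey only. The three uses of 400, the 15% oversampling allowance and the stated accrual cannot all be true. About 471 would be needed at time 1 for 400 completers, or 460 at 13% dropout, against a planned 350 to 420. The likely two-wave sample is about 298 to 357, or 340 if 400 enrol.

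This assumes that dropout applies to those enrolled at time 1, that it reaches the allowed 15%, and that WP1 participants are counted within the accrual. Relaxing the first two to the more lenient inflation or to 13% does not bring the requirement down to 420.

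The severity is minor to moderate. The stated number is wrong as written, but no power calculation in the protocol depends on 400 people at time 2, and 340 is within the protocol's own range for the model.

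**What to change.** State a separate target for each wave in section 2.4.1: 400 at time 1, which needs about 57 to 58 per month and so lies within the stated range, and about 340 with both surveys after 15% loss. Then:

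- replace the final sample size wording, so that 400 is clearly the time-1 number;
- rewrite the 15% oversampling sentence to say that the loss is accepted and leaves about 340, keeping replenishment for non-completion at time 1;
- correct the WP2 row of Appendix 1, so that it no longer has all 400 completing the survey twice;
- base the longitudinal precision statement on about 340 two-wave completers;
- say whether WP1 participants count towards the stated accrual.

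The cost is a few restated figures and no extra enrolment. The longitudinal sample looks slightly less favourable on paper. If the sponsor wants 400 at time 2 instead, the protocol must state 471 at time 1 and an accrual of about 67 per month, or a longer recruitment period. Section 2.4.2 needs no change on this account.
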